6.0 Study Drug Duration and Compliance

6.1 Study Drug Duration

Induction Period 1

For the safety population SA2, duration of exposure to study drug will be summarized for each treatment group in Induction Period 1.

Duration of exposure in Induction Period 1:

- If the subjects enrolled into Study M16-066 after the Induction Period 1:
 - Duration of exposure = min (the first study drug dose date in Study M16-066 – the first study drug dose date in Induction Period 1, the last study drug dose date in the Induction Period 1 – the first study drug dose date in the Induction Period 1 + 28 days),
- If the subject enrolled into Induction Period 2 after Induction Period 1:
 - Duration of exposure = min (the first study drug dose date in the Induction Period 2 – the first study drug dose date in Induction Period 1, the last study drug dose date in Induction Period 1 – the first study drug dose date in Induction Period 1 + 28 days),
- Otherwise:
 - Duration of exposure = the last study drug dose date in Induction Period 1 – the first study drug dose date in Induction Period 1 + 28 days.

For each treatment group and total in Induction Period 1, the duration of exposure will be summarized by the number of subjects treated, as well as the mean, standard deviation, median, minimum and maximum values. In addition, the number and percentage of subjects exposed to study drug will be summarized for the following exclusive duration intervals:

- 1 – 28 days
- 29 – 56 days
- 57 – 84 days

- 85 – 112 days
- > 112 days

Induction Period 2

For the safety population SA2_P2, the duration of exposure to study drug will be summarized for each treatment group in Induction Period 2.

Duration of exposure in Induction Period 2:

- If the subjects enrolled into Study M16-066 after Induction Period 2:
 - Duration of exposure = min (the first study drug dose date in Study M16-066 – the first study drug dose date in Induction Period 2, the last study drug dose date in Induction Period 2 – the first study drug dose date in Induction Period 2 + 28 days [for IV dose] or 56 days [for SC dose]),
- Otherwise:
 - Duration of exposure = the last study drug dose date in Induction Period 2 – the first study drug dose date in Induction Period 2 + 28 days [for IV dose] or 56 days [for SC dose].

For each treatment group and total in Induction Period 2, the duration of exposure will be summarized by the number of subjects treated, as well as the mean, standard deviation, median, minimum and maximum values. In addition, the number and percentage of subjects exposed to study drug will be summarized for the following exclusive duration intervals:

- 1 – 28 days
- 29 – 56 days
- 57 – 84 days
- 85 – 112 days
- > 112 days

All Risankizumab

For SA2_ALL, the duration of exposure to study drug will be summarized for all risankizumab treatment group over the whole course of the study.

Duration of exposure for all risankizumab:

- If the subjects enrolled into Study M16-066:
 - Duration of exposure = min (the first study drug dose date in Study M16-066 – the first risankizumab dose date in this study, the last risankizumab dose date in this study – the first risankizumab dose date in this study + 28 or 56 days [depending on that the last dose is IV or SC]),
- Otherwise:
 - Duration of exposure = the last risankizumab dose date in this study – the first risankizumab dose date in this study + 28 or 56 days [depending on that the last dose is IV or SC].

The duration of exposure will be summarized by the number of subjects treated, as well as the mean, standard deviation, median, minimum and maximum values. In addition, the number and percentage of subjects exposed to risankizumab will be summarized for the following exclusive duration intervals:

- 1 – 28 days
- 29 – 56 days
- 57 – 84 days
- 85 – 112 days
- 113 – 140 days
- 141 – 196 days
- > 196 days

6.2 Study Drug Compliance

Treatment compliance is calculated as follows:

$$TC = \frac{\text{Total number of injections and/or infusions received}}{\text{Total number of injections and/or infusions planned}} \times 100\%$$

Treatment compliance will be summarized by treatment group for Induction Period 1 and Induction Period 2 based on SA2 and SA2_P2, respectively. Descriptive summary including mean, median, standard deviation, minimum, and maximum, will be provided.

In addition, number and percentage of subjects who received full volume and average infusion duration (hours) will be provided for subjects who received intravenous therapy. Total number of injections received will also be provided for subjects who received subcutaneous therapy.

7.0 Demographics, Baseline Characteristics, Medical History, and Prior/Concomitant Medications

Demographics, baseline or disease characteristics, medical history, and prior and concomitant medications will be summarized by treatment group and overall for the ITT2 and ITT2_P2 populations. Categorical variables will be summarized with the number and percentage of subjects; percentages will be calculated based on the number of non-missing observations. Continuous variables will be summarized with descriptive statistics (number of non-missing observations, mean and standard deviation, median, minimum and maximum).

7.1 Demographics and Baseline Characteristics

The following demographic, as measured at baseline of the study, will be summarized.

Continuous variables:

- Age (years)
- Body weight (kg)
- Body weight – Female (kg)
- Body weight – Male (kg)
- Height (cm)
- Height – Female (cm)
- Height – Male (cm)
- Body Mass Index (kg/m²)

Categorical variables:

- Sex (male, female)
- Age (18 - < 40, 40 - < 65, ≥ 65)
- Weight (< 60 kg, ≥ 60 kg)
- Race (American Indian/Alaska Native, Asian, Black or African American, Native Hawaiian or Other Pacific Islander, White, Multiple)
- Race (White, Non-White)
- Ethnicity (Hispanic or Latino, Not Hispanic or Latino)
- Tobacco use (Never, current, former, unknown)
- Alcohol use (Never, current, former, unknown)
- Region (as defined in)
- BMI category
 - Underweight [< 18.5 kg/m²]
 - Normal [≥ 18.5 and < 25 kg/m²]
 - Overweight [≥ 25 and < 30 kg/m²]
 - Obese [≥ 30 kg/m²]

The following baseline characteristics, as measured at baseline of the study, will be summarized.

Continuous variables:

- Blood Pressure (systolic/diastolic) (mmHg)
- Pulse (bpm)
- Respiratory Rate (RPM)
- Temperature (°C)
- IBDQ total score and its components
- Full Mayo score and its components (stool frequency, rectal bleeding, PGA, and endoscopy subscores)
- Partial Adapted Mayo score
- Adapted Mayo score
- hs-CRP (mg/L)
- Fecal Calprotectin (mg/kg)
- Albumin (g/L)
- Short Form 36 Health Survey (SF-36) and its components
- European Quality of Life 5 Dimensions 5 Levels (EQ-5D-5L)
- Functional Assessment of Chronic Illness Therapy-Fatigue (FACIT-F)
- WPAI and its components
- Ulcerative Colitis Symptoms Questionnaire (UC-SQ)
- Disease duration (years)

Categorical variables (unless otherwise stated, the categorical variables regarding medication use are assumed to be UC-related):

- Advanced Therapy-IR status (yes, no),
 - The Advanced Therapy-IR is defined as documented intolerance or inadequate response to advanced therapy including one or more of the approved biologics for UC (infliximab, adalimumab, golimumab, ustekinumab, and/or vedolizumab) and/or approved JAK inhibitors for UC (tofacitinib, filgotinib, upadacitinib) and ozanimod.
- Number of prior failed advanced therapies (0, 1, 2, >2)

- Prior exposure to advanced therapy (yes, no) for non-Advanced Therapy-IR population
- Number of prior advanced therapies (≤ 1 or > 1) for Advanced Therapy -IR population
- Baseline corticosteroid use (yes, no)
- Baseline immunosuppressant use (yes, no)
- Baseline aminosalicylates use (yes, no)
- Prior exposure to anti-TNF for UC for non-Advanced Therapy-IR population (yes, no)
- Number of prior failed anti-TNF for UC (0, 1, 2, > 2) for Advanced Therapy-IR population
- Number of prior failed biologics for UC (0, 1, 2, > 2) for Advanced Therapy-IR population
- Mayo endoscopic subscore (2, 3)
- Baseline Adapted Mayo score (≤ 7 vs > 7)
- Baseline Partial Adapted Mayo score (≤ 4 vs > 4)
- Baseline Full Mayo score (≤ 9 vs > 9)
- Baseline hs-CRP (≤ 5 mg/L, > 5 mg/L)
- Baseline hs-CRP (\leq median, $>$ median)
- Disease duration (≤ 3 years, > 3 years)
- Disease duration (\leq median, $>$ median)
- Baseline Albumin (\leq median, $>$ median)
- Baseline Fecal Calprotectin (\leq median, $>$ median)
- Baseline Fecal Calprotectin (≤ 250 mg/kg, > 250 mg/kg)
- Baseline presence of pancolitis (yes, no)
- Disease extent (left-sided, extensive/pancolitis, limited to rectum)

In addition, some clinical tests at baseline such as TB test and electrocardiogram assessment will be summarized.

7.2 Medical History

Medical history data will be coded using the Medical Dictionary for Regulatory Activities (MedDRA). The actual version of the MedDRA coding dictionary will be noted in the statistical tables and clinical study report. The number and percentage of subjects in each medical history category (by MedDRA system organ class and preferred term) will be summarized overall and by treatment group based on the ITT2 and ITT2_P2 populations. The system organ class (SOC) will be presented in alphabetical order, and the preferred terms will be presented in alphabetical order within each SOC. Subjects reporting more than one condition/diagnosis will be counted only once in each row (SOC or preferred term). In addition, any subject with the UC disease extent record "left-sided," "extensive/pancolitis" or "limited to rectum" will be counted as having "colitis ulcerative" (preferred term) within gastrointestinal disorders (SOC).

7.3 Prior and Concomitant Medications

Prior and concomitant medications including UC specific medications (biologics, corticosteroids, aminosalicylates, immunosuppressant agents, and antibiotics) will be summarized by generic name.

A prior medication is defined as any medication taken prior to the date of the first dose of study drug. This includes medications with a start date before the first study drug administration date, regardless of the end date of these medications. Medications taken on the day of the first dose of study drug are not counted as prior medications. Summary on prior medication will be provided for ITT2.

A concomitant medication is defined as any medication that started prior to the date of the first dose of study drug and continued to be taken after the first dose of study drug or any medication that started on or after the date of the first dose of study drug, but not after the date of the last dose of study drug plus 140 days. The number and percentage of subjects taking medications will be summarized by generic drug name based on the World Health Organization (WHO) Drug Dictionary for both prior and concomitant medications.

Summary on concomitant medication will be provided for Induction Period 1 and Induction Period 2 based on ITT2 and ITT2_P2 respectively.

8.0 Handling of Potential Intercurrent Events

The primary efficacy endpoint of clinical remission per Adapted Mayo score at Week 12 (defined in Section 3.1) and the secondary efficacy endpoints (defined in Section 3.2) will be analyzed based on the ITT2 population. The following methods will be used to address potential intercurrent events (IEs):

- IE1. Premature discontinue from the study drug:
 - Data collected will be used regardless of premature discontinuation of study drug.
- IE2. Initiation or dose escalation of UC-related corticosteroid event defined as:
 - Subjects not on UC-related corticosteroids (systemic or locally acting corticosteroids for UC) at baseline who then initiated UC-related corticosteroids during the Induction study.
 - Subjects on UC-related systemic corticosteroids at baseline who have dosages increased to greater than the prednisone equivalent dose of corticosteroid taken at baseline, or initiation of any rectal corticosteroids during the Induction study regardless of rectal corticosteroid dose.
 - Subjects on UC-related rectal corticosteroids at baseline who have dosages increased to greater than the dose taken at baseline, or initiation of any new type of rectal or any systemic corticosteroids during the Induction study.

The time point of the UC-related corticosteroids intercurrent event is defined as the date when one of the scenarios above occurs for a subject. As such, subjects will be considered as "non-responder" for binary endpoints on or after the date of the UC-related corticosteroids intercurrent event through the end of the Induction study in the primary analysis (except for the occurrence of UC-related hospitalization and UC-related surgeries). For continuous endpoints, all measurements on or after the date of the UC-related corticosteroids intercurrent event through the end of the Induction study will not be used in the primary analysis.

- IE3. UC-Related Surgery (ileostomy, colectomy, or proctocolectomy):
The time point of the UC-related surgery (ileostomy, colectomy, or proctocolectomy) intercurrent event is defined as the date of the first UC-related surgery. All measurements on or after the date of the UC-related surgery (ileostomy, colectomy, or proctocolectomy) will be handled similarly as UC-related corticosteroid intercurrent events.

For the additional Period 1 efficacy endpoints and Induction Period 2 efficacy endpoints similar methods to address potential intercurrent events will be applied.

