5.2.1 Inclusion Criteria

1. Males or females \geq 18 and \leq 80 years of age, or minimum age of adult consent according to local regulations at the Baseline Visit. Sub-Study 2 only: Where locally permissible, subjects 16 to $<$ 18 years of age who meet the definition of Tanner Stage 5 for development (refer to Appendix G) at the Baseline Visit.
2. Confirmed diagnosis of UC for at least 3 months prior to Baseline. Appropriate documentation of biopsy results consistent with the diagnosis of UC or in the assessment of the Investigator, must be available.
3. Active UC with an Adapted Mayo score of 5 to 9 points and endoscopic subscore of 2 to 3 (confirmed by central review).
4. Demonstrated intolerance or inadequate response to one or more of the following categories of drugs: aminosalicylates, oral locally acting steroids, systemic steroids (prednisone or equivalent), immunomodulators, and/or biologic therapies
 - Demonstration of intolerance requires no minimum dose or duration of use.
 - Inadequate response is defined as outlined below:
 - Oral aminosalicylates (e.g., mesalamine, sulfasalazine, olsalazine, balsalazide):
 - Signs and symptoms of persistently active disease, in the opinion of the Investigator, during a current or prior course of at least 4 weeks of

treatment with 2.4 g/day mesalamine (2 g/day if controlled release), 4 g/day sulfasalazine, 1 g/day olsalazine, or 6.75 g/day balsalazide,

- Oral locally acting steroids (e.g., budesonide, beclomethasone):
 - Signs and symptoms of persistently active disease in the opinion of the Investigator, during or after a course of at least 4 weeks of treatment with 9 mg/day budesonide or 5 mg/day beclomethasone,
or
 - Inability to taper oral budesonide to at or below 6 mg/day without recurrent active disease,
- IV or Oral systemic steroids (prednisone or equivalent):
 - Signs and symptoms of persistently active disease in the opinion of the Investigator, during or after tapering of at least one regimen consisting of a dose equivalent to prednisone \geq 40 mg/day orally for 3 weeks or intravenously for 1 week,
or
 - Inability to taper oral systemic steroids at or below a dose equivalent to prednisone 10 mg/day without recurrent active disease,
- Immunomodulators:
 - Signs and symptoms of persistently active disease in the opinion of the Investigator, during a current or prior course of at least 90 days of treatment with one or more of the following:

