5.2.2 Exclusion Criteria

1. Subject with a current diagnosis of Crohn's disease (CD) or IBD-unclassified (IBD-U) or a history of radiation colitis or ischemic colitis.

Concomitant Medications and Treatments

2. Subject on oral UC-related antibiotics who has not been on stable doses for greater than, or discontinued within, 14 days prior to Baseline.
3. Subject on oral aminosalicylates who has not been on stable doses for greater than, or discontinued within, at least 14 days prior to Baseline.

4. Subject taking oral corticosteroids:
 - Budesonide > 9 mg/day
 - Beclomethasone > 5 mg/day
 - Prednisone or equivalent > 20 mg/day
 - Or has not been on the current course for \geq 14 days prior to Baseline and on a stable dose for \geq 7 days prior to Baseline
5. Subject on immunomodulators (AZA, 6-MP, MTX) who:
 - Has not been on the course for \geq 42 days prior to Baseline, and
 - Has not been on a stable dose for \geq 35 days prior to Baseline

Medications and Treatments During the Screening Period

6. Subject who received IV anti-infectives within 35 days prior to Baseline visit or oral anti-infectives (non-UC-related) within 14 days prior to the Baseline visit. This does not apply to TB prophylaxis.
7. Subject who received any parenteral nutrition within 35 days prior to Baseline.
8. Subject who received any live bacterial or viral vaccination within 35 days (8 weeks for Japan) prior to Baseline.
9. Subject who received cyclosporine, tacrolimus, or mycophenolate mofetil within 35 days prior to Baseline.
10. Subject who received fecal microbial transplantation within 35 days prior to Baseline.

Prior Medications and Treatments

11. Subject who received any:
 - approved biologic agent (e.g., infliximab, adalimumab, golimumab, vedolizumab) within 8 weeks prior to Baseline.
 - tofacitinib within 35 days prior to Baseline

- any investigational agent or procedure within 35 days or 5 half-lives prior to the Baseline, whichever is longer or
- subject who is currently enrolled in another interventional clinical study

12. Subject with prior exposure to p40 inhibitors (e.g., ustekinumab [Stelara]) or p19 inhibitors (e.g., risankizumab).

13. Subject has been taking combination of two or more of the following oral budesonide, oral beclomethasone, and/or oral prednisone (or equivalent) simultaneously, with the exception of inhalers, within 14 days prior to Screening or during the Screening period.

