2.2 Study Design Overview

Study M16-067 Sub-Study 2 is a Phase 3, multicenter, randomized, double-blind, placebo-controlled study designed to evaluate the efficacy and safety of risankizumab as

induction therapy in adult subjects with moderately to severely active UC, defined as Adapted Mayo score of 5 – 9 points (using the Mayo scoring system, excluding Physician's Global Assessment) with an endoscopic subscore of 2 or 3 on screening endoscopy, confirmed by central review.

Sub-Study 2 will enroll subjects who have had an intolerance or inadequate response (IR) to prior biologic therapy (bio-IR) and subjects who have not had an intolerance or inadequate response to prior biologic therapy (non-bio-IR). The bio-IR enrollment in Sub-Study 2 will be approximately 541 subjects and the non-bio-IR enrollment will be approximately 425 subjects.

The bio-IR population is defined as subjects with documented intolerance or inadequate response to one or more of the approved biologics for UC (infliximab, adalimumab, golimumab, and/or vedolizumab) or tofacitinib. The non-bio-IR population will include subjects who had an inadequate response or intolerance to conventional therapy.

Conventional therapy is defined as one or more of the following: aminosalicylates, oral locally acting steroids (e.g., budesonide, beclomethasone), systemic corticosteroids (prednisone or equivalent), or immunomodulators. This population will also include subjects who have received biologic therapy or tofacitinib in the past but stopped therapy based on reasons other than inadequate response or intolerance (e.g., change in reimbursement coverage, well-controlled disease).

The study duration may be up to 45 weeks, including a Screening period of approximately 35 days, a 12-week Induction Period 1, a 12-week Induction Period 2 for those subjects who do not achieve clinical response at Week 12, and a 140-day follow-up period from the last dose of study drug.

[figure not shown]
Sub-Study 2 Induction Period 1:

Subjects (n = 966) who meet all of the inclusion criteria and none of the exclusion criteria will be enrolled into the double-blind 12-week study and randomized in a 2:1 ratio to one of the following treatment groups:

- Group 1: Risankizumab 1200 mg IV Weeks 0, 4, 8 (n = 644)
- Group 2: Placebo IV Weeks 0, 4, 8 (n = 322)

The schematic of the Induction Period 1 is shown in [Figure 1](#).

Figure 1. Study Schematic of Induction Period 1

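### Read literally, the three-part steroid intercurrent-event definition in SAP 8.0 leaves out subjects whose only baseline UC steroid is oral budesonide or beclomethasone; the primary conclusion is very unlikely to change

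*SAP*

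**What the plan says.** SAP 8.0 lists three scenarios that make up IE2:

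- Bullet 1: "Subjects not on UC-related corticosteroids (systemic or locally acting corticosteroids for UC) at baseline who then initiated UC-related corticosteroids during the Induction study".
- Bullet 2: "Subjects on UC-related systemic corticosteroids at baseline who have dosages increased to greater than the prednisone equivalent dose" taken at baseline, or who start any rectal steroid.
- Bullet 3: "Subjects on UC-related rectal corticosteroids at baseline who have dosages increased to greater than the dose taken at baseline", or who start a new type of rectal steroid or any systemic steroid.

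The list is closed by the dating rule: "The time point of the UC-related corticosteroids intercurrent event is defined as the date when one of the scenarios above occurs for a subject".

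That date is used in several places:

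- SAP 9.2.1: the non-responder override, and the treatment of subjects in the tipping-point analysis.
- SAP 9.2.2: the return-to-baseline imputation for continuous endpoints.
- SAP 9.5.1: the censoring of time to clinical response.

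SAP 2.2 defines conventional therapy with two separate steroid entries: "oral locally acting steroids (e.g., budesonide, beclomethasone), systemic corticosteroids". Inclusion criterion 4 (Protocol 5.2.1) makes the same separation. On concomitant use, exclusion criterion 4 (Protocol 5.2.2) bars oral steroids only above a cap, for example "Budesonide > 9 mg/day", with a separate cap for beclomethasone. Exclusion criterion 13 bars a "Subject has been taking combination of two or more of the following oral budesonide, oral beclomethasone, and/or oral prednisone (or equivalent) simultaneously". Exclusion criterion 15 bars rectal steroids from 14 days before Screening.

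**The concern.** A baseline state that the entry criteria permit has no bullet, while bullet 3 serves a state that they exclude. If a subject on oral budesonide alone raises the dose or adds prednisone before Week 12, the literal rule sets no IE2 date. If the Week 12 criteria are then met, that subject counts as a remitter. For continuous endpoints, the post-change values stay in the analysis.

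The list is therefore narrower than its own heading and than the estimand wording in SAP 2.1, both of which speak of starting or escalating UC-related steroids without restricting the type. In practice the handling would depend on how the programmer classes the two drugs. A related gap is that bullets 2 and 3 do not clearly name a baseline systemic or rectal user who adds an oral locally acting steroid.

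The as-observed supplementary analysis in SAP 9.3.3 does not isolate the problem. It ignores IE2 for every subject, also changes the missing-data handling, and covers only the primary endpoint.

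**Working it through.** **Step 1. Baseline states against the bullets, read literally.**

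| Only UC steroid at baseline | Permitted at entry? | Bullet 1 | Bullet 2 | Bullet 3 |
|---|---|---|---|---|
| None | Yes | Yes | No | No |
| Oral systemic, within cap | Yes (exclusion 4) | No | Yes | No |
| Oral budesonide or beclomethasone, within cap | Yes (exclusion 4) | No | No | No |
| Rectal | No (exclusion 15) | No | No | Yes |

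Bullet 1 fails in the third row because its parenthesis requires no locally acting steroid either. Exclusion 13 means that these subjects should not also be on prednisone, which would have brought them under bullet 2.

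**Step 2. The plan's own figure.** SAP 2.4 states at least 90% power for 16% vs 6% remission with 644:322 subjects at two-sided 0.05. A pooled normal approximation gives 99.8%. Exact binomial power for an unpooled risk-difference test is 99.85%. That test is the planned Greenland-Robins variance taken as a single stratum, because no stratum counts are given. The stated floor is met with room to spare.

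**Step 3. How many subjects.** Let s be the share of subjects on an oral locally acting steroid alone, and e the share of those who start or escalate a steroid by Week 12. Both are assumptions. Events = 966 × s × e.

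- Low: 966 × 0.05 × 0.05 = 2.4.
- High: 966 × 0.15 × 0.10 = 14.5.
- Extreme: 966 × 0.20 × 0.20 = 38.6.

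**Step 4. Shift in the risk difference.**

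- Both arms at planning remission rates: s × e × 10 points, which is 0.025 points (low) to 0.15 points (high).
- All in one arm, with 30% of them remitters (assumed): 0.15 × 0.10 × 30 = 0.45 points; 0.20 × 0.20 × 30 = 1.2 points.
- All in one arm, every one a remitter: 0.20 × 0.20 × 100 = 4 points.

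**Step 5. Power under those shifts** (exact, same test as Step 2). A leak in the risankizumab arm means that the correctly derived rate is lower than 16%. A leak in the placebo arm raises the rate that the rule as written would show above 6%.

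| Scenario | Risankizumab vs placebo | Power |
|---|---|---|
| 0.45 points, risankizumab | 15.55% vs 6% | 99.7% |
| 0.45 points, placebo | 16% vs 6.45% | 99.6% |
| 1.2 points, risankizumab | 14.8% vs 6% | 99.3% |
| 1.2 points, placebo | 16% vs 7.2% | 98.7% |
| 4 points, risankizumab | 12% vs 6% | 89.2% |
| 4 points, placebo | 16% vs 10% | 76.9% |

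**Step 6. What would reverse a significant result.** Start from the planned counts, 103/644 vs 19/322. With the unpooled test, 60/644 gives a difference of 3.4 points (SE 0.0174, p = 0.0499) and 59/644 gives p = 0.0605. So 103 − 59 = 44 risankizumab remitters would have to be reclassified. A pooled score-type test needs 42. The extreme case has only 644 × 0.20 × 0.20 = 25.8 affected risankizumab subjects in all. If the observed effect were much smaller, losing 3 remitters would reverse significance only at observed counts of 60 to 62 (differences of 3.4 to 3.7 points), and losing 8 only at 60 to 67 (3.4 to 4.5 points).

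**The case against.** The best reply is that bullet 2 was meant to include every oral steroid. The split between locally acting and systemic comes from text on failed prior therapy. Where the protocol governs baseline concomitant use (exclusion criterion 4 and Protocol 5.2.3.2), it puts budesonide, beclomethasone and prednisone together as oral corticosteroids. On that view, bullets 2 and 3 simply mean non-rectal and rectal. This is plausible, and it stands as a possible intent. But the SAP nowhere states it, and bullet 1 of the same definition names locally acting alongside systemic steroids as distinct kinds. What survives is a defect of literal wording, not proof that the events would be missed.

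Three stronger readings are tempting and are not supported:

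- A reader might infer that the rule contradicts an independent estimand covering any steroid. SAP 2.1 does not use that word and refers back to Section 8.0 for the detail, so this is one incomplete list.
- The lack of a prednisone-equivalent conversion for budesonide might be taken as proof that it was left out. The documents give no conversion for any steroid.
- The Sub-Study 1 SAP (8.2) counts a dose increase of any UC-related steroid. It shows that simpler wording was available, but it is a separate plan and does not govern Sub-Study 2.

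It is also fair that starting or raising these steroids is prohibited (Protocol 5.2.3.2), and that such events may appear in the medication summaries (SAP 7.3) and deviation summaries (SAP Appendix A). Those tables do not change endpoint status.

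**Conclusion.** The gap is real on a literal reading and should be closed, but it is minor. Under the assumed ranges of 5–15% use and 5–10% events, about 2 to 14 of 966 subjects are affected, and at planning remission rates the primary difference moves by at most 0.15 points against a planned 10.

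A reader might take 98.7% as a lower limit on power. It is not: it holds only where 30% of the affected subjects remit. If every affected subject in one arm at 20% use and 20% events were a remitter, power would be about 89% (risankizumab arm) or 77% (placebo arm). None of these figures is a bound, because usage, event and remission rates are all assumed. The judgement that the primary conclusion is very unlikely to change rests on the planned effect size, the prohibition, and the 42 to 44 one-sided reclassifications needed at planned counts. The arithmetic covers the primary endpoint only; the same gap reaches the secondary and time-to-response analyses that use the IE2 date.

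**What to change.** Before unblinding, amend SAP 8.0 in three ways:

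- State which class oral budesonide and beclomethasone belong to for IE2.
- Make the list exhaustive. For a subject on any UC-related corticosteroid at baseline (oral systemic, oral locally acting or rectal), IE2 is a dose above baseline of that agent, or the start of any additional UC-related corticosteroid. This includes a second oral locally acting agent, such as beclomethasone added to budesonide.
- State how a switch between agents or types is counted. The existing prednisone-equivalent criterion can stay for switches between systemic agents.

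This is an analysis definition only; no treatment rule changes. The medication dates, doses and routes are already collected (Protocol 5.2.3.1). The cost is revised SAP wording, an updated derivation and a written switch rule. The downside is that a few subjects may move from responder to non-responder.
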